9.4.3 Safety Endpoints

Safety parameters are described in Section 4.2.1.3

Safety and tolerability will be assessed by clinical review of all relevant parameters including AEs, vital signs, laboratory safety tests and pulmonary function tests.

9.4.4 Derivations of Efficacy Endpoints

Computational details for selected efficacy endpoints in Sections 9.4.1 and 9.4.2 are provided below:

•
$$PVR = \frac{PAPmean - PCWP}{CO}$$
 (Wood Unit)

• Cardiac Index =
$$\frac{CO}{BSA} (L/min/m^2)$$

•
$$SVI = \frac{Stroke \ volume}{Body \ surface \ area} \ (mL/m^2)$$

- PAH-related mortality TTCW is defined as the time from randomization to the first occurrence of PAH-related death, PAH-related hospitalization, or disease progression.
- All-cause mortality TTCW is defined as the time from randomization to the first occurrence of all-cause death, PAH-related hospitalization, or disease progression.
- LPH physical dimension score = sum of scores from the questions 2, 3, 4, 5, 6, 7, 12, 13 in the LPH questionnaire (each scored 0 to 5 allowing a score in the range of 0 to 40) [Bonner, N., et al 2013].
- LPH total score = sum of all scores from the 21 questions in the LPH questionnaire (each scored 0 to 5 allowing a total score in the range of 0 to 105) [Bonner, N., et al 2013].

9.5 Analysis Populations

Although the analyses of the Phase 2 Cohort and Phase 3 Cohort will be performed separately, the definitions of analysis populations are the same for both cohorts.

9.5.1 Efficacy Analysis Population

The FAS population will serve as the primary population for all efficacy analyses. All randomized participants in the respective cohort who receive at least 1 dose of study treatment will serve as the basis for this population. For PVR and 6MWD, inclusion in the FAS population also requires having a baseline observation. For other efficacy endpoints except TTCW, inclusion in the FAS population requires having at least 1 observation (baseline or post-baseline). Participants will be included in the treatment group to which they are randomized.

9.5.2 Safety Analysis Population

Safety analyses will be conducted in the APaT population, which consists of all randomized participants who received at least one dose of study treatment. The analysis population will

be the same for analyses of both the Base and Extension Periods. Participants will be included in the treatment group corresponding to the study treatment they actually received for the analysis of safety data using the APaT population. This will be the treatment group to which they are randomized except for participants who take incorrect study treatment for the entire treatment period; such participants will be included in the treatment group corresponding to the study treatment actually received.

At least 1 laboratory, vital sign, or ECG measurement obtained subsequent to at least 1 dose of study treatment is required for inclusion in the analysis of the respective safety parameter. To assess change from baseline, a baseline measurement is also required.

9.6 Statistical Methods

Statistical testing and inference for safety analyses are described in Section 9.6.2. Efficacy results that will be deemed to be statistically significant after consideration of the Type I error control strategy are described in Section 9.8. Nominal *p*-values for secondary endpoints may be provided as an assessment of strength of evidence without intent to make inferential claims. All statistical tests will be conducted at the α =0.025 (one-sided) level.

For analysis purposes, the baseline assessment is considered the one closest to but before or on the day of randomization (Day 1).

9.6.1 Statistical Methods for Efficacy Analyses

This section describes the statistical methods that address the primary and secondary objectives. Methods related to the exploratory objectives will be described in the sSAP.

Efficacy analyses of the Phase 2 Cohort and the Phase 3 Cohort will be performed separately. The analyses at the end of the Extension Period will include data collected in both the Base and Extension Period of each study cohort. No statistical comparisons will be made for either Extension Period.

9.6.1.1 Phase 2 Cohort

In the Phase 2 Cohort, efficacy endpoints will be collected during the Base and Extension Periods. For the Base Period, the analysis timepoint of interest is Week 12. For the Extension Period, the analysis timepoint of interest is Week 24. Summary statistics will be provided for every planned data collection timepoint described in the SoA (Section 1.3).

Primary Endpoint

Following the ICH E9 (R1) guidance [European Medicines Agency 2020], The primary estimand for the primary objective used for the Phase 2 Cohort contains 5 attributes:

• The treatment condition of interest is MK-5475 or matching placebo with stable concomitant PAH-specific therapy, as defined in Section 5.1.

- The population of participants targeted by the clinical question are male/female participants with PAH between the ages of 18 and 75 years (inclusive).
- The variable to address the clinical question is PVR at Week 12.
- The following are intercurrent events, along with the approaches to handle them:
 - Death: hypothetical strategy to evaluate PVR at Week 12 as though death would not occur.
 - Treatment discontinuation: treatment policy strategy seeking to use every participant's actual Week 12 value, regardless of whether they are still taking study medication.

The approach to handling missing data for these intercurrent events is described below.

• The population-level summary is mean percent change from baseline in PVR at Week 12.

For this estimand, the primary approach will use a robust regression method to address the primary hypothesis. Robust regression method will be used because percent change from baseline in PVR is not expected to follow a normal distribution, based on other Phase 2 clinical trials which have used non-parametric methods for analyzing PVR [Simonneau, G., et al 2012] [Ghofrani, H. A., et al 2010]. The robust regression model will include terms for treatment and WHO-FC (Class II and Class III/IV). Missing PVR observations at Week 12 from participants in all treatment groups will be imputed following a PMM. Missing data due to death will be imputed as the worst outcome among all observed data. Missing data due to treatment discontinuation will be imputed based on the observed PVR observations at Week 12 from the placebo group referred as J2R (detailed below). If there are missing Week 12 data for other reasons, J2R will also be used. The randomization seed for imputations will be 5475007.

The difference (MK-5475 minus placebo) in percent change from baseline and the associated 95% CI and *p*-value will be provided. A *p*-value for the comparison of MK-5475 versus placebo <0.025 (one-sided) will be considered statistically significant contingent upon the multiplicity strategy (Section 9.8).

The following steps will be taken to perform the primary analysis, including imputation for missing data. Percent change from baseline in PVR at Week 12 is the response variable:

- 1. Define imputation model for different missingness patterns:
 - a. Obtain the worst outcome among all observed data.
 - b. Within the placebo group, for participants with both baseline and Week 12 data, fit an ANCOVA model including terms for treatment and WHO-FC (Class II and Class III/IV).

- 2. Impute missing data for different missingness patterns:
 - a. Death: for participants (in both treatment groups) who died before Week 12, the worst outcome among all observed data will be used to impute the missing Week 12 values.
 - b. Reasons other than death: For participants (in both treatment groups) missing the response variable, the fitted model in Step 1 will be used to impute the missing values.
- 3. Robust regression based on a Huber-type M estimator [Huber, P. J. 1973] will be performed for the imputed dataset. The model will include terms for treatment and WHO-FC (Class II and Class III/IV).
- 4. Steps 2 and 3 will be repeated 50 times to create 50 complete datasets and 50 sets of parameter estimates.
- 5. The final parameter estimate for the mean percent change will be the average of the 50 parameter estimates for the mean percent change from Step 4.
- 6. Steps 1 through 5 will be repeated 200 times based on bootstrap resampling. The resulting standard error for the mean percent change will be the standard error of the resulting parameter estimates obtained in the 200 bootstrap resampled datasets. The CI and *p*-value will be derived from a normal distribution based on the final parameter estimate and its standard error.

Two sensitivity analyses for percent change from baseline in PVR will be performed to assess the impact of missing data imputation. Within the same PMM structure in the primary analysis, for missing data due to reasons other than death, 1 analysis will use a tipping point approach and the other analysis will use an approach referred to as washout imputation.

In the tipping point approach, missing values due to reasons other than death will be imputed based on the first step in the primary analysis with a positive adjustment Δ added for the MK-5475 group. The inference will be carried out for a range of values of Δ . The smallest value of Δ that renders the significant result into a non-significant result will be the tipping point value, which provides a measure of robustness of the primary result.

In the washout imputation approach, missing values due to reasons other than death in the MK-5475 group will be imputed from a normal distribution with the expected value set to the baseline value in the MK-5475 group and standard deviation computed based on the root mean squared error from the ANCOVA model described in the primary analysis. Missing values in the placebo group will be imputed in the same way as in the primary analysis.

Secondary Endpoint

The primary approach for addressing the mean change from baseline in 6MWD at Week 12 will use the same robust regression method described above for the primary endpoint. Summary statistics will be provided for other selected hemodynamic parameters listed in

Section 9.4.1. Table 5 summarizes the analysis strategy for efficacy endpoints in the Phase 2 Cohort.

Endpoint	Туре	Statistical Method	Analysis Population	Missing Data Approach
Primary Endpoint				
Percent Change from baseline in PVR at Week 12	P Sen Sen	RR RR RR	FAS FAS FAS	PMM-J2R PMM-Tipping point PMM-Washout
Secondary Endpoints				
Change from baseline in 6MWD at Week 12	Р	RR	FAS	PMM-J2R
Change from baseline in selected hemodynamic parameters at Week 12	Р	SS	FAS	N/A

Table 5Analysis Strategy for Primary and Secondary Efficacy Endpoints in the Phase
2 Cohort

6MWD=6-minute walk distance; FAS=full analysis set; J2R=jump-to-reference; N/A=not applicable; P=Primary PMM=pattern mixture model; PVR=pulmonary vascular resistance; RR=robust regression; Sen=Sensitivity; SS=summary statistics.

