9.6.1.2 Phase 3 Cohort

In the Phase 3 Cohort, efficacy endpoints will be collected during the Base and Extension Periods. For the Base Period, the analysis timepoint of interest is Week 12. For the Extension Period, the analysis timepoint of interest is Week 24. Summary statistics will be provided for every planned data collection timepoint described in the SoA (Section 1.3).

Primary Endpoint

The primary estimand for the primary objective used for the Phase 3 Cohort contains 5 attributes:

- The treatment condition of interest is MK-5475 or matching placebo on background stable concomitant PAH-specific therapy, as defined in Section 5.1.
- The population of participants targeted by the clinical question are male/female participants with PAH between the ages of 18 and 75 years (inclusive).
- The variable to address the clinical question is 6MWD at Week 12.
- The following are intercurrent events, along with the approaches to handle them:
 - Death: hypothetical strategy to evaluate 6MWD at Week 12 as though death would not occur.

• Treatment discontinuation: treatment policy strategy seeking to use every participant's actual Week 12 value, regardless of whether they are still taking study medication.

The approach to handling missing data for these intercurrent events is described below.

• The population-level summary is mean change from baseline in 6MWD at Week 12.

For this estimand, the primary approach will use a robust regression method to address the primary hypothesis. Robust regression method will be used because change from baseline in 6MWD is not expected to follow a normal distribution, based on other Phase 3 clinical trials which have used non-parametric methods for analyzing 6MWD [Rubin, L. J., et al 2002] [Rubin, L. J., et al 2015]. The robust regression model will include a term for treatment and WHO-FC (Class II and Class III/IV). Missing 6MWD observations at Week 12 from participants in all treatment groups will be imputed following a PMM. Missing data due to death will be imputed based on the worst outcome among all observed data. Missing data due to treatment discontinuation will be imputed based on the observed 6MWD observations at Week 12 from the placebo group referred as J2R (detailed below). If there are missing Week 12 data for other reasons, J2R will also be used. The randomization seed for imputations will be 5475007.

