The difference in change from baseline and the associated 95% CI and *p*-value will be provided (MK-5475 minus placebo). A *p*-value for the comparison of MK-5475 versus placebo <0.025 (one-sided) will be considered statistically significant.

The following steps will be taken to perform the primary analysis, including imputation for missing data. Percent change from baseline in 6MWD at Week 12 is the response variable:

- 1. Define imputation model for different missingness patterns:
 - a. Obtain the worst outcome among all observed data.
 - b. Within the placebo group, for participants with both baseline and Week 12 endpoint, an MMRM model including terms for treatment and WHO-FC (Class II and Class III/IV) will be fit.
- 2. The same procedure in Steps 2 through 6 described in Section 9.6.1.1 will be used for analysis.

Two sensitivity analyses of the estimand for change from baseline in 6MWD will be performed to assess the impact of missing data imputation. Within the same PMM structure in the primary analysis, for missing data due to reasons other than death, 1 analysis will use a tipping point approach and the other analysis will use an approach referred to as washout imputation. The analysis approaches are the same as in the 2 sensitivity analyses described in Section 9.6.1.1 except the missing data due to reasons other than death will be imputed by the MMRM model in the primary analysis.

As a supplemental analysis, the primary analysis will be repeated, excluding participants who participated in the Phase 2 Cohort.

Secondary Endpoint

The primary approach for addressing the mean change from baseline in 6MWD at Week 24 will use the same robust regression method in Section 9.6.1.1. Summary statistics will be provided for the proportion of participants whose WHO-FC is not worse at Week 12 relative to baseline. Table 6 summarizes the analysis strategy for efficacy endpoints in the Phase 3 Cohort.

Endpoint	Туре	Statistical Method	Analysis Population	Missing Data Approach
Primary Endpoint				
Change from baseline in 6MWD at Week 12	P Sen Sen	RR RR RR	FAS FAS FAS	PMM-J2R PMM-Tipping point PMM-Washout
Secondary Endpoints				
Change from baseline in 6MWD at Week 24	Р	RR	FAS	PMM-J2R
Proportion of participants whose WHO functional class does not worsen at Week 12 relative to baseline.	Р	SS	FAS	N/A

Table 6	Analysis Strategy for Primary and Secondary Efficacy Endpoints in the Phase
	3 Cohort

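### Death is assigned a hypothetical strategy, but the primary analyses of both cohorts score it as the worst observed outcome, which is a composite strategy

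*Combined protocol and SAP*

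**What the plan says.** Section 9.6.1.1 sets out the Phase 2 primary estimand under ICH E9(R1) and names two intercurrent events, death and treatment discontinuation. Death gets a hypothetical "strategy to evaluate PVR at Week 12 as though death would not occur". The section then introduces its missing-data rules as the way these events are dealt with. For death the rule is: "Missing data due to death will be imputed as the worst outcome among all observed data". Steps 1a and 2a build this into the primary algorithm. For participants in any group who die before Week 12, "the worst outcome among all observed data will be used to impute the missing Week 12 values".

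Section 9.6.1.2 repeats the pairing for the confirmatory Phase 3 endpoint. The estimand reads "Death: hypothetical strategy to evaluate 6MWD at Week 12 as though death would not occur", the data rule reads "Missing data due to death will be imputed based on the worst outcome among all observed data", and the algorithm carries over: "The same procedure in Steps 2 through 6 described in Section 9.6.1.1 will be used for analysis".

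The tipping-point and washout sensitivity analyses operate "Within the same PMM structure in the primary analysis, for missing data due to reasons other than death". The handling of deaths is therefore the same in every listed analysis of the primary endpoints.

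**The concern.** A hypothetical strategy asks what Week 12 PVR or 6MWD would have been had the participant lived. Giving the participant the worst value recorded in the trial answers another question, because death itself becomes the bad outcome. The estimand paragraph and the algorithm therefore describe different quantities, in both cohorts.

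What is at stake is what the primary result may be said to show. The Phase 3 estimate would be labelled as the effect in a world without deaths, while the number carries a penalty for each death. An imbalance in deaths would move it, although the stated estimand says it should not. If the conflict is noticed only after deaths are known by arm, any choice between the two readings will look driven by the data.

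**Working it through.** **The passages side by side**

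| | Stated strategy for death | What the algorithm does |
|---|---|---|
| Phase 2, PVR (9.6.1.1) | hypothetical, no death | worst observed outcome (Steps 1a, 2a) |
| Phase 3, 6MWD (9.6.1.2) | hypothetical, no death | worst observed outcome (Step 1a, then Step 2a of 9.6.1.1) |
| Sensitivity analyses, both cohorts | not varied | non-death missingness only |

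Nothing in the documents links the worst value to a no-death scenario.

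**The plan's own power figures (Section 9.9.1)**

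Inputs: true effect 30 (percentage points or metres), drop-out about 10%, SD 0.4 or 70 m, 41 or 143 per group, one-sided alpha 0.025.

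- Planning effect: 30 × (1 − 0.10) = 27. All missing data are treated as jump-to-reference and none as worst outcome.
- Power = Φ(δ / (σ√(2/n)) − 1.960).
- Phase 2: 0.27 / (0.4 × √(2/41)) = 0.27 / 0.0883 = 3.056; Φ(1.096) = 86.4%, as stated.
- Phase 3: 27 / (70 × √(2/143)) = 27 / 8.28 = 3.262; Φ(1.302) = 90.3%, against the stated 90%.

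The arithmetic is right on its inputs. The conflict is one of definition.

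**Size of the conflict**

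The plan gives no expected death rate, so every death count below is an assumption. The simulations use normal data and a Huber M-estimator without the WHO-FC term. Deaths are imputed either as the worst observed value or at placebo level, the latter being one possible as-if-alive reading.

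Phase 3, 30 m effect, deaths the only missing data, 1,500 trials per case:

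| Deaths, MK-5475 / placebo | Worst value | Placebo level | Difference |
|---|---|---|---|
| 5 / 0 | 25.9 m | 29.1 m | −3.2 m |
| 0 / 5 | 34.2 m | 30.0 m | +4.2 m |

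The 29.1 m agrees with hand calculation: each MK-5475 death moved to placebo level should cost 30/143 = 0.21 m, so five give about 30 − 1.05 = 28.95 m. A smaller run (400 trials) with 0, 3, 5 and 7 MK-5475 deaths gave 29.7, 27.3, 25.5 and 23.8 m under the worst-value rule. That is (29.7 − 23.8)/7 = 0.84 m per death.

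With 10% missing per arm, as planned, and the deaths taken from within that 10% (1,500 trials per case in Phase 2, 600 in Phase 3):

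| Cohort | Deaths, MK-5475 / placebo | Placebo level | Worst value | Shift |
|---|---|---|---|---|
| Phase 2 | 1 / 0 | −27.25% | −26.25% | 1.0 point towards null |
| Phase 2 | 2 / 0 | −27.14% | −25.06% | 2.1 points towards null |
| Phase 2 | 0 / 1 | −27.27% | −28.91% | 1.6 points away from null |
| Phase 2 | 0 / 2 | −27.23% | −30.58% | 3.4 points away from null |
| Phase 3 | 3 / 0 | 26.85 m | 24.97 m | 1.9 m towards null |
| Phase 3 | 0 / 3 | 27.22 m | 29.77 m | 2.6 m away from null |

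Putting the shifted effects into the power formula, Phase 3 power is about 86% with three MK-5475 deaths (27 − 1.9 = 25.1 m) and about 95% with three placebo deaths (27 + 2.6 = 29.6 m). Huber weighting damps the shift without removing it: one MK-5475 death in Phase 2 moves a simple mean by 2.1 points and the Huber estimate by 1.0.

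**The case against.** The best defence is that the plan offers the worst value as a missing-data assumption inside a pattern-mixture model. A no-death value can never be observed, so some untestable assumption is needed, and 'had this person survived, the result would have been as poor as the worst seen' is one. But the documents do not say this. A reader has only a no-death label and a rule that penalises death.

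Three further points have weight.

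- **The comparator is chosen, not prescribed.** The plan names no as-if-alive value for deaths. Imputing MK-5475 deaths at their own arm's level would widen the five-death gap by about 5 × 30/143 = 1.05 m; a level poorer than placebo would narrow it.
- **The numbers are modest.** Five deaths against none within 12 weeks is a strong imbalance. The planned standard error is 8.28 m, so 3.2 m is about 0.39 standard errors. One MK-5475 death against none gives a gap of about 0.6 m, two against one about 0.4 m, and no deaths gives zero.
- **Relabelling leaves every estimate and p-value unchanged.** True, but it changes what those numbers may be claimed to estimate, which is what an estimand is for.

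A hypothetical strategy with a matching imputation would also be coherent. That is a second remedy, and no reason to leave the two texts in conflict.

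**Conclusion.** The inconsistency is real and appears in both cohorts. As written, the primary analyses implement a composite strategy for death under a hypothetical label, and no sensitivity analysis covers the stated target. The contradiction does not depend on how many participants die; its numerical effect does.

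For one or two deaths in a single Phase 2 arm, the estimate moves by about 1 to 3.4 percentage points. For three to five deaths in a single Phase 3 arm, it moves by about 2 to 4 m. The rule is not simply conservative: MK-5475 deaths pull the estimate towards the null and placebo deaths push it away. These sizes rest on assumed death counts, normal data, a simplified Huber model and, for the comparison, placebo-level imputation. The stated power figures reproduce and are not in question.

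This should be corrected, though it does not threaten the design.

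**What to change.** In Sections 9.6.1.1 and 9.6.1.2, change the strategy for death from hypothetical to composite, and define the variable as the Week 12 value, or the worst observed outcome if the participant has died by then. Say in the same sentence that 'worst' refers to the response variable being analysed. Steps 1a and 2a stay as they are.

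If the sponsor does want the no-death estimand, the alternative is to keep the hypothetical label and impute deaths by a model consistent with it, with the worst-value rule as a sensitivity analysis. That changes the primary analysis, so relabelling is the lighter course.

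Relabelling costs wording in two estimand paragraphs, with no new data or programming. Section 9 calls for a protocol amendment when primary hypotheses or their methods change before unblinding. The correction should be made on that timetable, before deaths by arm are known to those making it.

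### Both primary estimands are stated as means, but the only planned estimator is a Huber M-estimate, which is labelled a mean and need not equal one if the arms differ in distribution shape

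*Combined protocol and SAP*

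**What the plan says.** Section 9.6.1.1 sets out the Phase 2 primary estimand attribute by attribute under ICH E9(R1). The summary attribute reads: "The population-level summary is mean percent change from baseline in PVR at Week 12". Section 9.6.1.2 has the matching line for Phase 3: "The population-level summary is mean change from baseline in 6MWD at Week 12".

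The estimator is given in Step 3 of Section 9.6.1.1: "Robust regression based on a Huber-type M estimator", with terms for treatment and WHO functional class. Step 5 then names what comes out: "The final parameter estimate for the mean percent change will be the average of the 50 parameter estimates". Phase 3 takes this over: "The same procedure in Steps 2 through 6 described in Section 9.6.1.1 will be used for analysis".

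The reason given for the robust method is that "percent change from baseline in PVR is not expected to follow a normal distribution", and for Phase 3 that "change from baseline in 6MWD is not expected to follow a normal distribution". The plan does not say how the data will depart from normality. It gives no Huber tuning constant and no scale estimator.

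In Tables 5 and 6, the primary analysis and both sensitivity analyses of each primary endpoint use robust regression. They differ only in how missing values are imputed.

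**The concern.** A Huber estimate limits the influence of large residuals. For an asymmetric distribution it settles at a point other than the mean. Nothing in the plan explains why the treatment coefficient may be read as a difference in means, and no other planned analysis estimates that difference for the primary endpoints with the same imputation and adjustment. A reader of the study report would therefore see a figure called a mean that was not designed to estimate one.

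Two features make a pure shift doubtful. Percent change in PVR cannot fall below -100% but has no upper limit, so a drug that lowers PVR proportionally narrows the spread as well as moving the centre. The plan also sets deaths to the worst observed outcome, and the Huber fit then down-weights those values. If deaths are unbalanced between arms, the two summaries of the imputed data will differ.

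**Working it through.** **1. The plan's own power figures** (Section 9.9.1). With power = Φ(δ / (σ√(2/n)) − 1.96):
- Phase 2: δ = 0.27, σ = 0.4, n = 41. The standard error is 0.4 × √(2/41) = 0.0883, or 8.8 points. Power is 0.8635, against the stated 86.4%.
- Phase 3: δ = 27 m, σ = 70 m, n = 143. The standard error is 70 × √(2/143) = 8.3 m. Power is 0.9035, against the stated 90%.

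Both figures reproduce, and both come from a formula for a difference in means.

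**2. Comparison of the two contrasts.** Large simulated samples (500,000 or more per arm) give the difference in means and the two-arm Huber contrast. The tuning constant 1.345 and MAD scale are assumptions, because the plan gives neither. The WHO functional class term is left out. Distribution shapes and death rates are also assumptions.

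| Setting | Mean difference | Huber contrast |
|---|---|---|
| PVR, normal, shift of -30 points, 10% jump-to-reference | -26.9 | -27.0 |
| 6MWD, normal, shift of 30 m, 10% jump-to-reference | 27.1 m | 27.1 m |
| PVR, lognormal with SD 0.4, same shape in both arms | -30.0 | -30.0 |
| PVR, lognormal with log-SD 0.4, 30% proportional reduction, no missing data | -30.0 | -27.2 |
| Same, with 10% missing in each arm imputed normally from placebo | -27.0 | -25.3 |

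The third row shows that skew alone does not move the contrast. It does move the arm-level values: the placebo mean is 0.000 and its Huber value -0.038.

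**3. Why the proportional case differs.** At log-SD 0.385 without missing data, the active mean is -0.300 and its Huber value -0.321; the placebo mean is 0.000 and its Huber value -0.047. The offsets are unequal because the spreads are unequal. The Huber contrast is -0.321 − (-0.047) = -0.274, against -0.300 for the means.

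**4. Size under the planned imputation.** At log-SD 0.4 the gap is 27.0 − 25.3 = 1.7 points. That is 1.7/27.0 = 6% of the effect, and 1.7/8.8 = 0.2 of the planning standard error. The gap is about 2% at log-SD 0.3 and 11% at 0.5.

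**5. Direction.** For 6MWD with 10% jump-to-reference and deaths set to an assumed -300 m:
- 4% deaths on active, none on placebo: mean 14.0 m, Huber 22.3 m.
- None on active, 4% on placebo: mean 38.8 m, Huber 31.8 m.
- 2% in each arm: mean 26.3 m, Huber 26.9 m.

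The Huber contrast can therefore lie on either side of the mean difference.

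**The case against.** The strongest reply is that this is mostly labelling. The plan expects non-normal data, which includes symmetric heavy tails, and there the two contrasts agree. No passage predicts that shape will differ by arm. On the plan's own planning inputs the estimators coincide. In the proportional PVR example the Huber figure is the more conservative one, and the gap is small beside the sampling error. All of this stands, and it limits the size of the point. It does not remove the mismatch between the stated summary and the fitted quantity.

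Death is handled by a hypothetical strategy in both estimands, so down-weighting worst-value scores does not clearly move away from the stated target. That also stands. The death examples show that the two summaries of the imputed data can differ, not which is nearer the hypothetical quantity.

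A reader might infer several stronger things that the documents do not support:
- **That the plan expects skewed data.** It does not say so.
- **That dose choice would be distorted.** Section 4.2 bases selection on all safety and efficacy information. In the same lognormal model without missing data, reductions of 10, 20, 30 and 40% give Huber contrasts of -9.1, -18.1, -27.2 and -36.3 points, so dose order is kept.
- **That the Phase 3 claim depends on a mean reaching 30 m.** That figure is a clinical-relevance benchmark and planning value. The claim is superiority at one-sided 0.025.
- **That harm would be hidden.** Deaths, serious adverse events and discontinuations due to adverse events are reported by arm, and clinical worsening is adjudicated.

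Summary statistics are planned at each collection timepoint and might include arm means. The documents do not say so, and such means would not be the imputed, adjusted contrast.

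**Conclusion.** The point holds as a mismatch between estimand and estimator in both cohorts: the summary is a mean, the only primary-endpoint estimator is Huber regression, and its output is called a mean. Whether the reported number differs from the mean difference depends on whether distribution shape differs by arm, which the documents do not settle.

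Under the assumed proportional PVR effect with the plan's 10% missing data, the Huber contrast is about 6% smaller at log-SD 0.4, with a range of about 2% to 11% over log-SD 0.3 to 0.5. Unbalanced worst-value scores could produce larger gaps in either direction, but those rates are assumed. The results rest on tuning constant 1.345, MAD scale and no covariate.

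Neither the stated power nor the type I error is shown to be wrong. The consequence is confined to how the effect size is described and read.

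**What to change.** Keep the Huber test as the primary analysis in both cohorts, and make two changes in Sections 9.6.1.1 and 9.6.1.2:

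1. Add a prespecified supplementary analysis of each primary endpoint to Tables 5 and 6: ordinary least squares with the same terms (treatment and WHO functional class), fitted to the same 50 imputed datasets and the same bootstrap resamples, and reported as the mean difference.
2. Relabel the Step 5 output as a difference in Huber M-estimated location, and state the tuning constant and scale estimator. Without these the relabelled quantity is not fully defined. A sentence beside the population-level summary should say that the primary test concerns Huber location and that the supplementary fit estimates the mean difference.

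The cost is a few sentences and one extra model fit on datasets that will already exist. Sample size and alpha do not change. The downside is two effect estimates to present for each primary endpoint, so the plan should say beforehand that the Huber result carries the test.
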